6.6 Accountability procedures

The sponsor will provide the investigator with all necessary study supplies. Accountability for study supplies at the study site is the responsibility of the investigator.

Access to investigational medical devices will be controlled, and the investigational medical devices will be used only in the clinical investigation and according to the clinical study protocol. The sponsor will keep records to document the physical location of all investigational medical devices from shipment to the investigation sites until return or disposal. The PI or an authorized designee will keep records documenting the receipt, use, return, and disposal of the investigational medical devices, which will include the following:

1. The date of receipt.
2. Identification of each investigational medical device (batch number/serial number or unique code).
3. The expiry date (see [Section 6.2](#) for additional information).
4. The date or dates of use.
5. Subject identification number.
6. Date on which the investigational medical device was returned/explanted from subject, if applicable.
7. The date of return of unused, expired, or malfunctioning investigational medical devices (if applicable).

6.7 Level and method of blinding

In this split-face design, the treating investigator, the Merz NLF Scale evaluator (i.e., person responsible for assessing aesthetic effectiveness), and the study subject will be blinded to treatment assignment. The blinded evaluator cannot be the treating investigator or the study coordinator.

7 SAFETY AND ADVERSE EVENTS

7.1 Definitions

7.1.1 *Investigational medical device*

An investigational medical device is defined as a medical device being assessed for safety or effectiveness in a clinical investigation. This definition includes medical devices already on the market that are being evaluated for new intended uses, new populations, new materials, and/or design changes. In this protocol, the terms “investigational medical device” and “investigational device” are used interchangeably.

7.1.2 *Adverse event (AE)*

An AE is defined as an untoward medical occurrence, which does not necessarily have a causal relationship to the investigational medical device. An AE can therefore be any unfavorable, unintended, or untoward clinical sign (including an abnormal laboratory finding), unintended disease or injury, and/or a symptom or disease temporally associated with the use of the investigational medical device, whether or not considered related to that investigational medical device.

- Definition includes events related to the investigational medical device or the comparator.
- Definition includes events related to the procedures involved.
- AEs may include, but are not limited to, subjective or objective symptoms spontaneously offered by the subject, uncovered by review of concomitant medications or therapies, and/or observed by the investigation-site staff. The investigator will determine the description (sign, symptom, or diagnosis), onset, outcome, seriousness, severity, cause, and action taken for any event.

In cases of surgical or diagnostic procedures, the condition/illness leading to such a procedure is considered as the AE, rather than the procedure itself.

Pre-existing conditions that do not worsen during the course of the clinical investigation are not reportable as AEs. Recurring symptoms associated with pre-existing conditions are not considered AEs unless they have a clinically significant increase in severity and/or frequency. To determine whether a condition has worsened, it is compared to the condition of the subject at screening.

Elective treatments planned before screening, which are documented in the subject's source data, are not typically regarded as AEs. The subject's course must be monitored

until the event has subsided, or in a case of permanent impairment, until the event stabilizes and the overall clinical outcome has been ascertained.

7.1.3 Adverse device effect (ADE)

An ADE is defined as an adverse event related to the use of an investigational medical device.

- Definition includes AEs resulting from insufficient or inadequate instructions for use, deployment, implantation, installation, or operation, or any malfunction of the investigational medical device.
- Definition includes any event resulting from use error or from intentional misuse of the investigational medical device.

7.1.4 Serious adverse event (SAE)

A SAE is any adverse event that results in:

- Death
- Life-threatening illness or injury (or places the subject at immediate risk of death from this event as it occurred) or
- Hospitalization or prolonged hospitalization, or
- Disability/incapacity or permanent impairment of a body structure or a body function, or
- An important medical event for which medical or surgical intervention is required to prevent life-threatening illness or injury, or permanent impairment of a body structure or body function, or
- Fetal distress, fetal death, or a congenital abnormality/birth defect.

NOTE: Planned hospitalization for a pre-existing condition, or a procedure required by the protocol, without serious deterioration in health, is not considered an SAE. Pre-planned admissions must be recorded in the subject's source documentation.

If a subject experiences an additional AE that prolongs a pre-planned hospitalization, this event is considered to be an SAE and should be reported as an SAE.

In the case of a fatality, the primary cause of death (the event leading to death) is considered the SAE, and death is considered the outcome. "Fatal" will be recorded as the outcome. Death may be reported as an SAE only when no cause of death can be determined (e.g., sudden death, unexplained death).

7.1.5 *Serious ADE (SADE)*

A SADE is defined as a serious adverse event related to the use of an investigational medical device.

- Definition includes SAEs resulting from insufficient or inadequate instructions for use, deployment, implantation, installation, or operation or any malfunction of the investigational medical device.
- Definition includes any SAE resulting from use error or from intentional misuse of the investigational medical device.

7.1.6 *Unanticipated adverse device effect (UADE)*

A UADE is defined as:

- Any serious adverse effect on health or safety or any life-threatening problem or death caused by, or associated with, a device, if that effect, problem, or death was not previously identified in nature, severity, or degree of incidence in the investigational plan or application (including a supplementary plan or application), risk analysis report, Investigator's Brochure (IB), or product labeling, or
- Any other unanticipated serious problem associated with a device that relates to the rights, safety, or welfare of subjects.

7.1.7 *Anticipated serious adverse device effect (ASADE)*

An ASADE is defined as:

Any serious adverse effect which by its nature, severity, or degree of incidence or outcome has been identified in the risk analysis report, IB, or product labeling.

7.1.8 *Common treatment site responses (CTRs)*

CTRs are common clinical presentations and/or side effects that a study subject may experience following treatment. Subjects will self-report CTRs, as defined *a priori* in the protocol, on diary cards provided to them. The treating investigator will review and initial the diary and determine if any entries should be reported as AEs. A CTR that is more severe than what is generally expected and/or is not resolving should also be evaluated by the investigator as a possible AE, SAE, ADE, SADE, and/or UADE.

7.1.9 *Device deficiency*

A device deficiency is defined as any inadequacy of a medical device with respect to its identity, quality, durability, reliability, safety, or performance. Device deficiencies include malfunctions, use errors, and inadequate labeling.

Device deficiencies include events that did not lead to an AE, but could have led to a medical occurrence if suitable action had not been taken, if intervention had not been made, or if circumstances had been less fortunate.

All device deficiencies shall be documented and reported by the PI throughout the clinical investigation and appropriately managed by Merz North America, Inc. in accordance with [Sections 7.2.4.3](#) and [7.3](#).

7.1.10 *Malfunction*

Malfunction is defined as failure of an investigational medical device to perform in accordance with its intended purpose, when used in accordance with the product labeling or the protocol.

All device malfunctions shall be documented and reported by the PI throughout the clinical investigation and appropriately managed by Merz North America, Inc. in accordance with [Sections 7.2.4.3](#) and [7.3](#).

7.2 *Reporting requirements*

7.2.1 *Determining severity/intensity*

The investigator is required to grade the severity/intensity of each AE. The clinical severity/intensity of an AE will be classified as follows:

- ***Mild:*** Signs and symptoms that can be easily tolerated. Symptoms can be ignored and disappear when the subject is distracted.
- ***Moderate:*** Signs and symptoms that cause discomfort and interfere with normal functioning, but are tolerable. They cannot be ignored and do not disappear when the subject is distracted.
- ***Severe:*** Signs and symptoms that affect usual daily activity and incapacitate the subject, thereby interrupting his/her daily activities.

The definitions above are difficult to apply for some data (e.g., clinically relevant laboratory values that are documented and evaluated on the eCRF AE report form). In such situations, the investigator should exercise medical and scientific judgment.

7.2.2 Determining causal relationship

An AE is considered to be “related” to the investigational medical device if a causal relationship between the investigational medical device and the AE is at least a reasonable possibility (i.e., the relationship cannot be ruled out).

NOTE: The expression “reasonable causal relationship” is intended to convey that there are facts (evidence) or arguments to suggest a causal relationship. Otherwise, the relationship should be considered as “not related”.

7.2.3 Determining outcome

The reportable outcomes and/or sequelae of an AE may include the following:

- Recovered/resolved
- Recovering/resolving
- Not recovered/not resolved
- Recovered/resolved with sequelae
- Fatal
- Unknown

NOTE: If a subject experiences more than one AE, only the AE leading to death will be attributed with a “fatal” outcome.

7.2.4 Procedures for reporting specific events

7.2.4.1 Adverse event (AE) and adverse device effect (ADE)

Subjects will be carefully monitored during the clinical investigation for possible AEs and ADEs.

The period of observation for AEs and ADEs extends from signing of the informed consent form (ICF) until the subject’s last visit. Any medical occurrence between the time the ICF is signed and the first treatment with the investigational medical device is classified as an AE or ADE and must be documented in the subject’s file and in the eCRF. New AEs or ADEs reported to the investigator during the observational period (i.e., after the start of treatment with the investigational medical device) must also be documented, treated, and followed.

Any AE, ADE, and/or device deficiency observed during study conduct will be fully investigated, documented, and followed until the event is either resolved, until the

condition stabilizes, until the event is otherwise explained, or the subject is lost to follow-up.

The investigator will assess and record any AE or ADE in detail in the subject's file (medical record) and in the eCRF AE report form. At a minimum, the following information will be recorded:

- AE diagnosis or main symptom
- Location of AE: systemic or restricted to injection area. In case of local reaction, the corresponding area should be reported.
- Start and stop dates
- Severity/Intensity
- Causal relationship
- Serious (yes or no)
- Outcome
- Action taken with investigational medical device
- AE resulting in subject discontinuation (yes or no)

7.2.4.2 *Serious adverse event (SAE) and serious adverse device effect (SADE)*

The investigator must report all SAEs and SADEs that occur during the observational period on the SAE form, within 24 hours, whether considered related or not related to the investigational device.

The investigator must report SAEs and SADEs to Merz or designee as defined in [Section 7.2](#) and the site's IEC/IRB per their reporting guidelines.

Although all information required for completing an SAE report form may not be available within the specified time period, an initial report should be submitted and the following minimal information should be provided:

- An identifiable subject number;
- Adverse event;
- Investigational device name;
- Causality or relationship of investigational device; and/or
- Investigator/investigational site name.

Within 10 working days after Merz first receives notice of the SAE/SADE, Merz Product Safety will conduct an evaluation of the SAE/SADE and report the results of such evaluation to regulatory agencies, IECs/IRBs, and investigators, as applicable.

Follow-up SAE/SADE reports should be sent without delay to the sponsor or designee as an SAE form (marked as a “follow-up” report). The SAE/SADE has to be followed until the SAE/SADE is resolved/recovered or a plausible explanation is available.

In the case of a reportable death, the investigator shall make every effort to obtain a copy of the autopsy report and/or death certificate. The investigator will be required to review any post-mortem findings, including histopathology, and provide a synopsis of all pertinent findings by updating the SAE form.

SAEs/SADEs occurring after the end of the observational period would need to be reported if the investigator considers the event to be related to the investigational medical device. These reports generally will not be entered into the investigation database. Following the database lock for the study, all ongoing SAEs/SADEs will be followed until resolution or stabilization under the responsibility of the investigator per his/her standard of care.

7.2.4.3 *Technical device complaints*

For device deficiencies or device malfunctions, the investigator will attempt to evaluate if the deficiency or malfunction might have led to an AE if suitable action had not been taken, intervention had not been made, or circumstances had been less fortunate.

Complaints are defined as any written, electronic, or oral communication that alleges deficiencies related to the identity, quality, durability, reliability, safety, or performance of a medical device.

- A Device Technical Complaint form must be completed and submitted by the investigative site, irrespective of the seriousness of the case.
- A Device Technical Complaint form must be completed and submitted by the investigative site, irrespective of whether the complaint led to an AE.
- If a technical complaint is associated with an SAE, the investigative site must also complete and submit an SAE form (see [Section 7.2.4.2](#)) in addition to the Device Technical Complaint form. SAE forms for device clinical trials should be sent to Merz Product Safety for processing (as defined in [Section 7.3](#)).

Any technical complaints should be reported to the sponsor. The investigator will complete the Device Technical Complaint form and send **within 24 hours** to the Merz

Technical Complaint Department for processing using the following email address:
[contact].

7.2.4.4 *Pregnancy*

Any female subject who experiences pregnancy during the study must be reported by the investigator to Merz Product Safety or designee upon learning of the pregnancy. Pregnancies and pregnancy follow-up should be reported on a Pregnancy Report Form. Pregnancy follow-up should describe the outcome of the pregnancy, including any voluntary or spontaneous discontinuation; details of the birth; the presence or absence of any congenital abnormalities, birth defects, maternal or newborn complications, and their relation, if any, to the investigational medical device. Each pregnancy must be reported on the end of study eCRF.

7.4 Procedures for unblinding

Only the sponsor, the monitor, and the designee managing the electronic randomization system are unblinded in this study.

In the event of a medical emergency, where unblinding is determined to be necessary by the treating investigator, the medical monitor at the sponsor or designee will be contacted immediately to facilitate the identification of the Belotero Balance product (Test or Control) that was randomized to the NLF in question. In the event that unblinding becomes necessary, the treating investigator must adequately document the circumstances in the subject's source documents.

8 STATISTICAL METHODS

This section describes the statistical analyses foreseen at the time of study planning. Further details on the statistical and analytical aspects will be presented in the statistical analysis plan (SAP) that will be prepared and completed prior to database lock.

Any deviations from planned analyses, the reasons for such deviation, and all alternative or additional statistical analyses that may be performed before database close or unblinding, respectively, will be described in amendments to the clinical study protocol and/or the SAP. All deviations and/or alterations will also be summarized in the clinical study report.

8.1 Estimation of sample size

Sample size calculation was performed using the nQuery+nterim version 4.0 statistical software. Based on a review of comparable clinical literature [2][3][4][12][13][14][15], it is assumed for this power calculation that a change of 3.8 cm on a 10-cm VAS represents a clinically meaningful difference in pain as experienced between lidocaine-treated and non-lidocaine-treated NLFs. Assuming a statistical power, $1-\beta$ of 95%, a one-sided level of significance of $\alpha = 0.025$, and a conservative estimate of standard deviation of difference of 7, a total of 47 subjects will be required. To account for possible subject dropout after randomization and prior to treatment (up to 10% attrition), a total of 52 subjects will be enrolled, yielding approximately 104 total NLFs (52 Test and 52 Control). Additionally, a minimum of 20% of the enrolled total sample size will consist of subjects in the Fitzpatrick Skin Types IV, V, or VI group. Subjects from the Fitzpatrick skin type IV, V, and VI group will be approximately evenly distributed within the IV, V, and VI categories.

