3.2 Study assessments and definitions

3.2.1 *Effectiveness assessments*

3.2.1.1 *Evaluation of pain*

Pain will be assessed using a visual analog scale (VAS) [\[9\]](#)[\[10\]](#)[\[11\]](#); this VAS includes 21-numbered circles at 0.5 cm increments, spanning 10 cm total, and is anchored by word descriptors (see Figure 2). The level of pain will be evaluated for each NLF independently immediately upon completion of injection (time zero) [REDACTED] [REDACTED] on Day 1. Time zero will be defined as the time the last injection needle is removed from each NLF, separately, after a full correction on Day 1. At time zero, the subject will be asked to rate the pain experienced throughout the injection

procedure in a given NLF. For all other intervals, subjects will be asked to rate the pain experienced at that specific time point.

At the specified Day 1 assessment times, subjects will be presented with the VAS and asked to circle the one (1) number that best describes their pain level. Subjects will have access to their previous scores during the rating process.

Figure 2: Example of a visual analog scale (VAS) for the right NLF at time zero on Day 1

0 minutes

Immediately after administration of the time-zero pain VAS, subjects will be asked to assess their treatment preference with respect to pain. The Subject Pain-Preference Assessment will include questions similar to the following:

1. Was one treatment less painful than the other? (yes or no)
2. If answered yes, which side was less painful? (right or left)
3. If answered yes to question 1: Based on the difference in pain you felt between the two sides, would you choose one treatment over the other in the future? (yes, no, or no preference).

The treating investigator or study coordinator will verbally query the subject and subsequently record the Subject Pain-Preference Assessment responses in the source documents and enter in the eCRF.

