4.2 Inclusion criteria

In order to be eligible for study participation, each subject must meet all of the following criteria:

1. Has right and left NLF ratings of 2 or 3 (moderate or severe) on the Merz NLF Scale, as determined by the blinded evaluator (i.e., a qualified healthcare practitioner delegated by the treating investigator).
2. Has the same Merz NLF Scale rating on both NLFs (i.e., symmetrical NLFs).
3. Is a candidate for bilateral NLF treatment with Belotero Balance.
4. Is at least 18 years of age at the time of screening.
5. Has an adequate understanding (reading, speaking, and writing) of the local/regional language.
6. Is willing and able to give written informed consent after having been informed of the requirements and the restrictions of the study.
7. Understands and accepts the obligation not to receive any other procedures (i.e., dermal fillers, toxin treatments, facial ablative or fractional laser, microderm abrasion, chemical peels, non-invasive skin-tightening [e.g., Ultherapy, Thermage], or surgical procedures) below the orbital rim on the face during study participation.
8. Is willing to comply with all requirements of the study, including being photographed, following post-treatment care instructions, and attending all study visits.

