5 STUDY PROCEDURES

5.1 Schedule of events by visit

The Schedule of Events is presented in [Appendix 11.1](#).

Visit 1 – Screening/Enrollment (Day 1/Baseline)

The following procedures will be performed at Visit 1:

Pre-treatment assessments:

- Obtain written informed consent. A subject must be informed of the study requirements, including the risks and benefits of participation. An IEC/IRB-approved informed consent must be signed and dated by the subject prior to any study-related activities or procedures being performed, including discontinuation of any prohibited medications.
- Record demographics/medical history.
- Review and record concomitant medications/procedures.
- Perform urine pregnancy test (if female of childbearing potential). Negative test required prior to randomization.
- Have blinded evaluator (i.e., a qualified healthcare practitioner delegated by the treating investigator and trained by the sponsor) independently perform the Merz Nasolabial Fold (NLF) Scale assessment.
 - **NOTE:** Every effort should be made to ensure that the same blinded evaluator perform the NLF scale assessment at each visit.
- Take standardized NLF baseline photographs.
- Treating physician confirms that the subject meets all eligibility criteria prior to randomization.
- Recall that no anesthesia or other methods to minimize pain (e.g., Tylenol®, ice or ice compress, topical anesthetic, local nerve block) are allowed before NLF injection. *That is, no pre-treatment forms of facial pain reduction are allowed on Day 1.*
- Randomize subject to Belotero Balance injections (Test or Control product by NLF, Subject's right or left NLF injected first). All subject randomization codes will be generated by an electronic system.
- [REDACTED]

Injection and accompanying assessments:

- Administer treatment injections, **not to exceed the maximum allowable injection volume of 3 mL per NLF over the two treatment sessions (initial injection on Day 1 and optional touch-up injection at Week 2).**
 - Document volume injected into each fold (right and left) in the eCRF.
 - Document injection technique (i.e., serial puncture and/or linear threading) in the eCRF.
 - **NOTE:** The same injection technique must be used for both NLFs on Day 1.
- Administer VAS pain assessment for each NLF at time zero (i.e., the time the last injection needle is removed from each NLF, separately, after a full correction).

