6.3 Study treatment

All protocol-specific criteria for the administration of study treatment must be met and documented prior to administration of any study treatment. All device administration (injection) will be performed on site by the principal investigator (PI); only the PI can inject. The PI is also described as the treating investigator in this document. Subjects will not be dispensed any investigational material. Any noncompliant subject or site may be discontinued from the study ([Section 5.2](#)).

6.3.1 *Planned treatment procedure and administration*

Subjects will receive treatment with Belotero Balance with integral lidocaine (Test product) and Belotero Balance without lidocaine (Control product).

At baseline, approximately 52 subjects will be randomized in this split-face study. Prior to injection, one NLF will be randomized to receive Belotero Balance with integral lidocaine (Test), and the contralateral NLF will receive Belotero Balance without lidocaine (Control).

A single randomization scheme will determine which NLF (subject's right or left) will be assigned to Test product or Control product and which NLF (subject's right or left) will be injected first. Randomization will be provided by an electronic randomization system, which site personnel must access following confirmation that the subject meets all eligibility criteria.

Care must be taken to follow the subject's randomization assignment – ensuring the Test product and Control product syringes are injected according to their assigned order (Test first or Control first) and into the NLF that is randomly assigned to be injected first (subject's right NLF first or subject's left NLF first). Accurate documentation of (1) which product (Test or Control) is injected into which NLF (subject's right or left) and (2) in the order assigned by the randomization system

(subject's right NLF first or subject's left NLF first) is of critical importance in this study.

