4 DETERMINATION OF SAMPLE SIZE

Sample size calculation was performed using the nQuery+nterim version 4.0 statistical software. Based on a review of comparable clinical literature ([2-8]), it is assumed for this power calculation that a change of 3.8 cm on a 10-cm VAS represents a clinically meaningful difference in pain as experienced between lidocaine-treated and non-lidocaine-treated NLFs. Assuming a statistical power, $1-\beta$ of 95%, a one-sided level of significance of $\alpha = 0.025$, and a conservative estimate of standard deviation of difference of 7, a total of 47 subjects will be required to be enrolled into the trial. In order to accommodate likelihood of potential subject dropout after randomization and prior to treatment (up to 10% attrition), a total of 52 subjects will be enrolled, yielding approximately 104 total NLFs (52 Test and 52 Control). Additionally, a minimum of 20% of the enrolled total sample size will consist of subjects in the Fitzpatrick Skin Types IV, V, or VI group. Subjects from the Fitzpatrick skin type IV, V, and VI group will be approximately evenly distributed within the IV, V, and VI categories.

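### Does a planning SD of 7 on a 0–10 cm pain scale undermine the stated 47 subjects and 95% power?

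*Protocol*

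**What the plan says.** Protocol 8.1 takes from a literature review that "a change of 3.8 cm on a 10-cm VAS represents a clinically meaningful difference in pain". It sets one-sided alpha at 0.025 and power at 95%, and then uses "a conservative estimate of standard deviation of difference of 7, a total of 47 subjects will be required". SAP 4 repeats the input: "a conservative estimate of standard deviation of difference of 7, a total of 47 subjects will be required to be enrolled". Both sections raise 47 to 52 to allow up to 10% loss between randomization and treatment. Neither gives a unit, a reference of its own, a per-fold SD or a between-fold correlation for the 7.

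The instrument is bounded. Protocol 3.2.1.1 states that "this VAS includes 21-numbered circles at 0.5 cm increments, spanning 10 cm total". The primary analysis is a one-sided paired t-test on Test minus Control (Protocol 8.4.1.1, SAP 7.1.1).

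The design makes the two folds of a subject alike. Protocol 4.2 requires equal baseline severity ratings on both sides, Protocol 5.1 adds that "The same injection technique must be used for both NLFs on Day 1", and under Protocol 6.3 "only the PI can inject".

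**The concern.** A paired design is chosen because a person's two ratings tend to move together, which shrinks the SD of their difference. Here the planning SD is 7 on a scale only 10 cm long. That exceeds the largest value the scale permits at a 3.8 cm difference when the correlation is zero or positive. If the input cannot be expected from this design, the printed 47 and 95% do not describe the trial that will be run, and a reader cannot see why 52 people are injected. A sample size built on a faulty SD can also leave a trial underpowered, so the direction of the error has to be checked.

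**Working it through.** **Inputs.** From Protocol 8.1 and SAP 4: difference 3.8, SD of difference 7, one-sided alpha 0.025, power 95%. From Protocol 3.2.1.1: scores between 0 and 10 cm. The between-fold correlation rho is not in the documents; rho ≥ 0 is an assumption.

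**1. The plan's own figure.** Paired t-test, noncentral t with n − 1 degrees of freedom and noncentrality (3.8/7)·√n. Power is 0.9497 at n = 46 and 0.9538 at n = 47, so 47 reproduces. It does so only if 7 is in the same unit as 3.8, which settles the unit as cm. For attrition, 47 × 1.10 = 51.7, rounded up to 52.

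**2. Ceiling on the SD if rho ≥ 0.** A score on 0–10 with mean m has variance at most m(10 − m). With Test mean m and Control mean m + 3.8, the variance of the difference is at most m(10 − m) + (m + 3.8)(6.2 − m). This peaks at m = 3.1: 21.39 + 21.39 = 42.78, and √42.78 = 6.54 cm.

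**3. Ceiling at any correlation.** The difference lies between −10 and 10 with mean 3.8, so its variance is at most 100 − 14.44 = 85.56, and √85.56 = 9.25 cm. An SD of 7 is therefore attainable.

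**4. What an SD of 7 requires.** Let D be Control minus Test, so E[D²] = 49 + 14.44 = 63.44.
- Correlation: rho = (42.78 − 49)/42.78 = −0.145 or lower.
- Share of subjects with folds at least 5 cm apart: at least (63.44 − 25)/75 = 51%.
- Share rating the lidocaine fold worse: D² ≤ 10|D| gives E|D| ≥ 6.344. The mean of max(−D, 0) is then at least (6.344 − 3.8)/2 = 1.272, so the share is at least 12.7%.

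Such data would be surprising here, but they cannot be ruled out.

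**5. Effect on the required number** (noncentral t, 95% power, before attrition; SDs of 5 and 4 are assumptions):

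| SD (cm) | N |
|---|---|
| 7 | 47 |
| 6.54 | 41 |
| 5 | 25 |
| 4 | 17 |

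With the plan's allowance, 41 × 1.10 = 45.1, rounded up to 46. The like-for-like gap at the ceiling is 52 − 46 = 6 subjects.

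**6. How firm the ceiling figures are.** An SD of 6.54 with rho ≥ 0 arises in only one way: every score is 0 or 10, the folds are independent, and the means are 3.1 and 6.9. Then D is +10 with probability 0.69² = 0.476, −10 with probability 0.31² = 0.096, and 0 otherwise (0.428). Enumerating the paired t-test over this three-point distribution gives:

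| n | Normal theory | Exact |
|---|---|---|
| 41 | 95.3% | 94.2% |
| 47 | 97.4% | 96.6% |
| 52 | 98.4% | 97.8% |

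The normal-theory figures are approximations, not guarantees. At this ceiling, 41 falls just short of 95% and 47 still exceeds it.

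**The case for a change.** The strongest case for a change is that calling a value conservative does not supply a source. A conservative SD should sit at the upper end of what is plausible, and this one lies beyond what non-negative correlation allows. The section also does not show what the trial can detect. With 52 analysed, the smallest significant observed difference is t(0.975, 51) × SD/√52 = 2.008 × SD/7.211. That is 0.84 cm at SD 3, 1.39 cm at SD 5 and 1.82 cm at SD 6.54, or 22% to 48% of 3.8 cm. Success could be declared on a reduction well under the stated meaningful difference. At an SD of 5 or 4 the trial is about twice the size the primary test needs, or more.

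Part of this stands. The SD has no printed unit or source of its own, and 7 cm is implausibly large for two folds of one person. But it does not follow that the plan itself implies 41 or fewer: that needs rho ≥ 0, which neither document states, and setting 41 against 52 compares a figure before attrition with one after it. Nor is the evidence on correlation all one way. Protocol 6.3.1.1 lets angle, depth, quantity and the number of injection sites vary, and Protocol 3.2.1.1 lets subjects see their previous scores. That differences below 3.8 cm can be significant follows from testing against zero, and a different SD in the sample-size paragraph would not alter that rule. SAP 7.1 and 7.1.1 provide for 95% confidence limits and a summary of the Test minus Control difference, so readers will see the size of the effect.

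**Conclusion.** No change follows. The calculation is right for its inputs, and the unit can be recovered from it. The planning SD errs in the safe direction, and the documents say so. A true SD below 7 raises power and leaves the type I error untouched, because the t-test uses the observed SD. Assuming non-negative correlation, the excess is 6 enrolled subjects at the ceiling. It is larger if the true SD is nearer 4 or 5 cm, but no figure in the documents fixes that. Even in the extreme distribution at the ceiling, 47 subjects give 96.6% power. Adding a unit, a source or a sensitivity range would be good practice, but N, test, success rule and conclusion would all remain the same. This is a generous planning value with missing detail, not a fault in the plan.
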